9.2.1. Serious Adverse Events

An SAE is any AE from this study that results in one of the following:

- death;
- initial or prolonged inpatient hospitalization;
- a life-threatening experience (that is, immediate risk of dying);
- persistent or significant disability/incapacity;
- congenital anomaly/birth defect;
- events considered significant by the investigator based upon appropriate medical judgment.

Study site personnel must alert Lilly, or its designee, of any SAE within 24 hours of investigator awareness of the event via a sponsor-approved method. If alerts are issued via telephone, they are to be immediately followed with official notification on study-specific SAE forms. This 24-hour notification requirement refers to the initial SAE information and all follow-up SAE information.

Although all AEs are recorded in the eCRF after signing informed consent, SAE reporting begins after the subject has signed informed consent and has received investigational product. However, if an SAE occurs after signing informed consent, but prior to receiving Investigational product (IP), AND is considered reasonably possibly related to a study procedure then it MUST be reported.

Investigators are not obligated to actively seek AEs or SAEs in subjects once they have discontinued from and/or completed the study (the subject summary CRF has been completed). However, if the investigator learns of any SAE, including a death, at any time after a subject has been discharged from the study, and he/she considers the event reasonably possibly related to the study treatment or study participation, the investigator must promptly notify Lilly.

Pregnancy (maternal or paternal exposure to IP) does not meet the definition of an adverse event. However, to fulfill regulatory requirements any pregnancy should be reported following the SAE process to collect data on the outcome for both mother and fetus.

9.2.1.1. Suspected Unexpected Serious Adverse Reactions

Suspected unexpected serious adverse reactions (SUSARs) are serious events that are not listed in the IB and that the investigator identifies as related to IP or procedure. United States 21 CFR 312.32 and European Union Clinical Trial Directive 2001/20/EC and the associated detailed guidances or national regulatory requirements in participating countries require the reporting of SUSARs. Lilly has procedures that will be followed for the recording and expedited reporting of SUSARs that are consistent with global regulations and the associated detailed guidances.

9.2.2. Complaint Handling

Lilly collects product complaints on IPs and drug delivery systems used in clinical trials in order to ensure the safety of study participants, monitor quality, and to facilitate process and product improvements.

Subjects should be instructed to contact the investigator as soon as possible if he or she has a complaint or problem with the IP so that the situation can be assessed.

9.3. Treatment of Overdose

For the purposes of this study, an overdose of LY3337641 is considered any dose higher than the planned study dose. There is no specific antidote for LY3337641. In the event of overdose, the subject should receive appropriate supportive care and any AEs should be documented.

9.4. Safety

9.4.1. Laboratory Tests

For each subject, laboratory tests detailed in [Appendix 2](#) should be conducted according to the Schedule of Activities (Section 2).

9.4.2. Vital Signs

For each subject, vital signs measurements should be conducted according to the Schedule of Activities (Section 2).

Blood pressure and pulse rate should be measured after at least 5 minutes supine.

Unscheduled orthostatic vital signs should be assessed, if possible, during any AE of dizziness or posture-induced symptoms. Additional vital signs may be measured during each study period if warranted and agreed by the investigator.

9.4.3. Electrocardiograms

For each subject, ECGs should be collected according to the Schedule of Activities (Section 2).

Any clinically significant findings from ECGs that result in a diagnosis and that occur after the subject receives the first dose of the IP, should be reported to Lilly, or its designee, as an AE via eCRF.

For each subject, a single 12-lead digital ECG will be collected according to the Schedule of Activities. Electrocardiograms must be recorded before collecting any blood for safety or pharmacokinetic tests. Subjects must be supine for approximately 5 to 10 minutes before ECG collection and remain supine but awake during ECG collection. Electrocardiograms may be obtained at additional times, when deemed clinically necessary. All ECGs recorded should be stored at the investigational site.

Electrocardiograms will be interpreted by a qualified physician (the investigator or qualified designee) at the site as soon as possible after the time of ECG collection, and ideally while the subject is still present, to determine whether the subject meets entry criteria at the relevant

visit(s) and for immediate subject management, should any clinically relevant findings be identified.

If a clinically significant finding is identified (including, but not limited to, clinically significant changes in QT/QTc interval from baseline) after enrollment, the investigator will determine if the subject can continue in the study. The investigator, or qualified designee, is responsible for determining if any change in subject management is needed, and must document his/her review of the ECG printed at the time of collection. Any new clinically relevant finding should be reported as an adverse event.

9.4.4. Safety Monitoring

The Lilly CP/CRP/clinical research scientist will monitor safety data throughout the course of the study.

Lilly will review SAEs within time frames mandated by company procedures. The Lilly clinical pharmacologist or research physician will consult with the functionally independent Global Patient Safety medical physician or clinical research scientist when appropriate, and periodically review:

- trends in safety data;
- laboratory analytes;
- AEs.

9.5. Pharmacokinetics

At the visits and times specified in the Schedule of Activities venous blood samples of approximately 2 mL each will be collected to determine the plasma concentrations of LY3337641. A maximum of 2 samples per treatment period may be collected at additional time points if warranted and agreed upon between both the investigator and sponsor. Instructions for the collection and handling of blood samples will be provided by the sponsor. The actual date and time (24-hour clock time) of each sampling will be recorded.

9.5.1. Bioanalysis

Samples will be analyzed at a laboratory approved by the sponsor and stored at a facility designated by the sponsor.

Concentrations of LY3337641 will be assayed using a validated liquid chromatography with tandem MS detection methods.

Bioanalytical samples collected to measure LY3337641 concentrations will be retained for a maximum of 1 year following last subject visit for the study.

9.6. Pharmacodynamics

This section is not applicable for this study.

9.7. Genetics

A blood sample will be collected for pharmacogenetic analysis as specified in the Schedule of Activities, where local regulations allow.

Samples will not be used to conduct unspecified disease or population genetic research either now or in the future. Samples will be used to investigate variable response to LY3337641 and to investigate genetic variants thought to play a role in rheumatoid arthritis. Assessment of variable response may include evaluation of AEs or differences in exposure.

All samples will be coded with the subject number. These samples and any data generated can be linked back to the subject only by the investigative site personnel.

Samples will be retained for a maximum of 15 years after the last subject visit, or for a shorter period if local regulations and/or the ethical review board (ERB)/institutional review board (IRBs) impose shorter time limits, for the study at a facility selected by Lilly or its designee. This retention period enables use of new technologies, response to regulatory questions, and investigation of variable response that may not be observed until later in the development of LY3337641 or after LY3337641 is commercially available.

Molecular technologies are expected to improve during the 15 year storage period and therefore cannot be specifically named. However, existing approaches include whole genome or exome sequencing, genome wide association studies, multiplex assays, and candidate gene studies. Regardless of technology utilized, data generated will be used only for the specific research scope described in this section.

9.8. Biomarkers

This section is not applicable for this study.

9.9. Health Economics

This section is not applicable for this study.

10. Statistical Considerations and Data Analysis

10.1. Sample Size Determination

Up to 32 subjects may be enrolled in order to ensure that 24 subjects complete all 4 study periods.

The sample size chosen will provide a precision of 8% for the estimate of the geometric mean ratio in AUC between the test formulations versus the reference formulation, and between the test formulations administered in the fed versus the fasted state. It means that there is a 90% probability that the half-width of the resulting 90% confidence interval (CI) of the geometric mean ratio in AUC is no larger than 8%. No direct estimate of intra-subject variability is available.

The sample size chosen will provide a precision of 13% for the estimate of the geometric mean ratio in C_{max} between the test formulations versus the reference formulation, and between the test formulations administered in the fed versus the fasted state. It means that there is a 90% probability that the half-width of the resulting 90% CI of the geometric mean ratio in AUC is no larger than 13%. No direct estimate of intra-subject variability is available.

Based on Study JPDD, the coefficient of variation (CV%) for AUC and C_{max} were approximately 30% and 50%, respectively, for a 20-mg dose of LY3337641 administered. Assuming that half of the total CV% is contributed by intra-subject variability, an approximation of the intra-subject variability of 15% for AUC and 25% for C_{max} .

Subjects who are randomized but not complete all 4 treatment periods may be replaced to ensure that enough subjects complete the study. The replacement subject will assume the withdrawn subject's treatment sequence (receiving each treatment allocated).

10.2. Populations for Analyses

10.2.1. Study Participant Disposition

A detailed description of subject disposition will be provided at the end of the study.

10.2.2. Study Participant Characteristics

The subjects' age, sex, weight, height, and other demographic characteristics will be recorded and summarized using descriptive statistics.

10.3. Statistical Analyses

Statistical analysis of this study will be the responsibility of Eli Lilly and Company or its designee.

Pharmacokinetic analyses will be conducted on the full analysis set. This set includes all data from all randomized subjects receiving at least one dose of the IP according to the treatment the subjects actually received. Safety analyses will be conducted on the safety population, defined as all randomized subjects receiving at least one dose of the IP, whether or not they completed all protocol requirements.

Additional exploratory analyses of the data will be conducted as deemed appropriate.

10.3.1. Safety Analyses

10.3.1.1. Clinical Evaluation of Safety

All drug-related and procedural AEs will be listed, and if the frequency of events allows, safety data will be summarized using descriptive methodology.

The incidence of symptoms for each treatment will be presented by severity and by association with IP as perceived by the investigator. Symptoms reported to occur prior to enrollment will be distinguished from those reported as new or increased in severity during the study. Each symptom will be classified by the most suitable term from the medical regulatory dictionary.

The number of drug-related SAEs will be reported.

10.3.1.2. Statistical Evaluation of Safety

Safety parameters that will be assessed include clinical laboratory parameters, vital signs, and ECGs. The parameters will be listed and summarized using standard descriptive statistics, as appropriate. Additional analysis will be performed if warranted upon review of the data.

10.3.2. Pharmacokinetic Analyses

10.3.2.1. Pharmacokinetic Parameter Estimation

Pharmacokinetic parameter estimates for LY3337641 will be calculated by standard noncompartmental methods of analysis and reported by treatment period.

The primary parameters for analysis will be C_{\max} and AUC from time zero to infinity ($AUC[0-\infty]$), and AUC from time zero to time t , where t is the last time point with a measurable concentration ($AUC[0-t_{\text{last}}]$). The t_{\max} will be observed from the data. Other noncompartmental parameters, such as half-life associated with the terminal rate constant in noncompartmental analysis ($t_{1/2}$), apparent total body clearance of drug calculated after extra-vascular administration (CL/F), and apparent volume of distribution during the terminal phase after extra-vascular administration (V_z/F) may be reported.

10.3.2.2. Pharmacokinetic Statistical Inference

Pharmacokinetic parameter estimates for LY3337641 will be compared between formulations and between the fed and fasted states. Log-transformed C_{\max} and the AUC estimates will be analyzed using a linear mixed-effects model with PK estimate as response variable, treatment, period, and sequence as fixed effects; and a random effect for subject. The treatment differences will be back-transformed to present the ratios of geometric means and the corresponding 90% CI.

The t_{\max} will be analyzed non-parametrically. Median of differences and approximate 90% CI for the median of differences will be calculated for the fed versus fasted states and for the comparisons between the different formulations.

10.3.3. Interim Analyses

An interim analysis is scheduled to occur after approximately 24 subjects complete the first 3 periods to support an internal formulation decision for clinical planning activities associated with LY3337641. The primary purpose of this interim analysis is to compare the AUC(0-∞) and C_{max} of T1_{fasted} and R_{fasted}, however all available PK data will be evaluated during the interim. After Period 3, crossover data from approximately 12 subjects for these 2 treatments should be available. A sample size of 12 subjects will provide a precision of 13% and 20% for the estimate of the geometric mean ratio in AUC and C_{max}, respectively, between the two formulations. Assumptions are the same as detailed in Section 10.1. An additional interim analysis after Period 4 and before the final database lock may be conducted if needed.

11. References

Appendix 1. Abbreviations and Definitions

Term	Definition
AE	adverse event: Any untoward medical occurrence in a patient or clinical investigation subject administered a pharmaceutical product that does not necessarily have a causal relationship with this treatment. An AE can therefore be any unfavorable and unintended sign (including an abnormal laboratory finding), symptom, or disease temporally associated with the use of a medicinal (investigational) product, whether or not related to the medicinal (investigational) product.
API	active pharmaceutical ingredient
AUC	area under the concentration versus time curve
AUC(0-∞)	AUC from time zero to infinity
AUC(0-t_{last})	AUC from time zero to time t, where t is the last time point with a measurable concentration
BTK	Bruton's tyrosine kinase
CI	confidence interval
CL/F	apparent total body clearance of drug calculated after extra vascular administration
C_{max}	maximum observed drug concentration
complaint	A complaint is any written, electronic, or oral communication that alleges deficiencies related to the identity, quality, purity, durability, reliability, safety or effectiveness, or performance of a drug or drug delivery system.
compliance	Adherence to all the trial-related requirements, good clinical practice (GCP) requirements, and the applicable regulatory requirements.
confirmation	A process used to confirm that laboratory test results meet the quality requirements defined by the laboratory generating the data and that Lilly is confident that results are accurate. Confirmation will either occur immediately after initial testing or will require that samples be held to be retested at some defined time point, depending on the steps required to obtain confirmed results.
CP	Clinical Pharmacologist
CRF	case report form
CRP	Clinical Research Physician: Individual responsible for the medical conduct of the study. Responsibilities of the CRP may be performed by a physician, clinical research scientist, global safety physician or other medical officer.
CRU	clinical research unit
ECG	electrocardiogram
enroll	The act of assigning a subject to a treatment. Subjects who are enrolled in the trial are those who have been assigned to a treatment.

enter	Subjects entered into a trial are those who sign the informed consent form directly or through their legally acceptable representatives.
ERB	ethical review board
FDA	Food and Drug Administration
FSH	follicle-stimulating hormone
GCP	good clinical practice
HIV	human immunodeficiency virus
IB	Investigator's Brochure
ICF	informed consent form
ICH	International Conference on Harmonization
IND	Investigational New Drug: An application to the FDA to allow testing of a new drug in humans.
informed consent	A process by which a subject voluntarily confirms his or her willingness to participate in a particular trial, after having been informed of all aspects of the trial that are relevant to the subject's decision to participate. Informed consent is documented by means of a written, signed and dated informed consent form.
Investigational product (IP)	A pharmaceutical form of an active ingredient or placebo being tested or used as a reference in a clinical trial, including products already on the market when used or assembled (formulated or packaged) in a way different from the authorized form, or marketed products used for an unauthorized indication, or marketed products used to gain further information about the authorized form.
investigator	A person responsible for the conduct of the clinical trial at a trial site. If a trial is conducted by a team of individuals at a trial site, the investigator is the responsible leader of the team and may be called the principal investigator.
Non-investigational product (non-IP)	A product that is not being tested or used as a reference in the clinical trial, but is provided to subjects and used in accordance with the protocol, such as: concomitant or rescue/escape medication for preventative, diagnostic, or therapeutic reasons, medication to ensure adequate medical care, and/or products used to induce a physiological response.
open-label	A study in which there are no restrictions on knowledge of treatment allocation, therefore the investigator and the study participant are aware of the drug therapy received during the study.
PK	pharmacokinetic(s)
PSD	particle size distribution
SAE	serious adverse event

screen	The act of determining if an individual meets minimum requirements to become part of a pool of potential candidates for participation in a clinical trial.
SUSARs	suspected unexpected serious adverse reactions
$t_{1/2}$	half-life associated with the terminal rate constant in noncompartmental analysis
TEAE	treatment-emergent adverse event: Any untoward medical occurrence that emerges during a defined treatment period, having been absent pretreatment, or worsens relative to the pretreatment state, and does not necessarily have to have a causal relationship with this treatment
t_{max}	time to the maximum observed drug concentration
V_z/F	apparent volume of distribution during the terminal phase after extra vascular administration

Appendix 2. Clinical Laboratory Tests

Laboratory Tests

Hematology ^a	Clinical Chemistry ^a
Hematocrit	Sodium
Hemoglobin	Potassium
Erythrocyte count (RBC)	Chloride
Mean cell volume	Calcium
Mean cell hemoglobin	Phosphorus
Mean cell hemoglobin concentration	Fasting glucose
Leukocytes (WBC)	Urea
Absolute counts of:	Uric acid
Neutrophils	Total protein
Lymphocytes	Albumin
Monocytes	Total bilirubin
Eosinophils	Alkaline phosphatase (ALP)
Basophils	Aspartate aminotransferase (AST)
Platelets	Alanine aminotransferase (ALT)
	Creatinine
	Gamma-glutamyl transferase (GGT)
	Lactate dehydrogenase (LDH)
	Hepatitis B surface antigen ^{b,c}
	Hepatitis C antibody ^{b,c}
	HIV ^{b,c}
	Pregnancy test
	FSH ^b
Urinalysis ^a	
Specific gravity	
pH	
Protein	
Glucose	
Ketones	
Bilirubin	
Urobilinogen	
Blood	
Nitrite	
Leukocytes	
Microscopic examination of sediment (test only if dipstick result is abnormal and per investigator's discretion)	

Abbreviations: FSH = follicle-stimulating hormone; HIV = human immunodeficiency virus; RBC = red blood cells; WBC = white blood cells.

^a Results will be reported and validated by the local lab at the time of testing.

^b Performed at screening only if clinically indicated and per investigator's discretion.

^c Tests may be waived if they have been performed within 6 months before screening with reports available for review.

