6.2. Exclusion Criteria

Subjects will be excluded from study enrollment if they meet any of the following criteria at screening and/or enrollment:

- [8] are investigative site personnel directly affiliated with this study and their immediate families. Immediate family is defined as a spouse, biological or legal guardian, child, or sibling
- [9] are Lilly employees
- [10] are currently enrolled in a clinical trial involving an investigational product or any other type of medical research judged not to be scientifically or medically compatible with this study
- [11] have participated, within the last 30 days, in a clinical trial involving an investigational product. If the previous investigational product has a long half-life, 3 months or 5 half-lives (whichever is longer) should have passed
- [12] have previously completed or withdrawn from this study or any other study investigating LY3337641, and have previously received the investigational product
- [13] have known allergies to LY3337641, related compounds or any components of the formulation, or history of significant atopy
- [14] have an abnormality in the 12-lead ECG that, in the opinion of the investigator, increases the risks associated with participating in the study
- [15] have an abnormal blood pressure as determined by the investigator
- [16] have significant history of or current cardiovascular, dermatological (such as eczema, psoriasis, and acne), respiratory, hepatic, renal, gastrointestinal (cholecystectomy is not acceptable), endocrine, hematological, or neurological disorders capable of significantly altering the absorption, metabolism, or elimination of drugs; of constituting a risk when taking the investigational product; or of interfering with the interpretation of data
- [17] have known or ongoing psychiatric disorders
- [18] regularly use known drugs of abuse

- [19] show evidence of human immunodeficiency virus (HIV) infection and/or positive human HIV antibodies
- [20] show evidence of hepatitis C and/or positive hepatitis C antibody
- [21] show evidence of hepatitis B and/or positive hepatitis B surface antigen
- [22] are women who are lactating
- [23] have used or intend to use over-the-counter or prescription medication, including herbal medications, within 14 days prior to planned dosing
- [24] have donated blood or had blood loss of more than 450 mL within 3 months of screening

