6.4. Screen Failures

Individuals who do not meet the criteria for participation in this study (screen failure) may not be re-screened.

7. Treatment

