8.1.1. Discontinuation of Inadvertently Enrolled Subjects

If the Sponsor or investigator identifies a subject who did not meet enrollment criteria and was inadvertently enrolled, a discussion must occur between the Lilly CP/CRP and the investigator to determine if the subject may continue in the study. If both agree it is medically appropriate to continue, the investigator must obtain documented approval from the Lilly CP/CRP to allow the inadvertently enrolled subject to continue in the study with or without continued treatment with investigational product.

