Appendix 4. Blood Sampling Summary

This table summarizes the approximate number of venipunctures and blood volumes for all blood sampling (screening, safety laboratories, and bioanalytical assays) during the study. Fewer venipunctures and blood draws may actually occur, but this will not require a protocol amendment.

Protocol I8K-MC-JPDF Sampling Summary

Purpose	Maximum Blood Volume per Sample (mL)	Maximum Number of Blood Samples	Maximum Total Volume (mL)
Screening tests ^a	17	1	17
Clinical laboratory tests ^a	11	13	143
Pharmacokinetics ^b	2	76	152
Pharmacogenetics	10	1	10
Total			322
Total for clinical purposes [rounded up to nearest 10 mL]			330

^a Additional samples may be drawn if needed for safety purposes.

^b Includes up to 2 additional samples per treatment period.

Leo Document ID = 703e9077-f89a-47f5-82ab-b423ca236f45

Approver: PPD
Approval Date & Time: 09-Jan-2017 13:48:54 GMT
Signature meaning: Approved

Approver: PPD
Approval Date & Time: 09-Jan-2017 13:53:47 GMT
Signature meaning: Approved

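### Appendix 2 footnote b leaves HIV, hepatitis B and hepatitis C serology optional, so the positive-result limb of exclusions [19] to [21] can go unchecked

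*Protocol*

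**What the plan says.** Three exclusion criteria in Protocol Section 6.2 concern blood-borne viral infection. Criterion [19] removes subjects who "show evidence of human immunodeficiency virus (HIV) infection and/or positive human HIV antibodies". The next two criteria are built the same way: [20] for hepatitis C, with the antibody as its test, and [21] for hepatitis B, with the surface antigen as its test. Each has two limbs: evidence of infection, and a positive serological result.

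Appendix 2 of the Protocol lists hepatitis B surface antigen, hepatitis C antibody and HIV, each with markers b and c. Footnote b reads "Performed at screening only if clinically indicated and per" the investigator's discretion. Footnote c reads "Tests may be waived if they have been performed within 6 months before screening with reports available for review". FSH carries b alone. The pregnancy test carries neither.

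The SAP does not deal with eligibility testing.

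**The concern.** The positive-result limb can operate only if someone runs the test. Footnote b makes that depend on a clinical indication in people who, under inclusion criterion [1], must already be judged healthy on history and examination. An indication will seldom arise in that population, and where it does the evidence-of-infection limb may already apply. The serology limb adds most for the silent carrier, who is the subject most likely to go untested.

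At stake is subject safety. The drug is an irreversible BTK inhibitor, and Section 3.2 notes that BTK loss-of-function mutations in humans reduce B-cell and immunoglobulin levels. The sponsor treats infection and immune status as eligibility matters elsewhere too: recent herpes zoster, tuberculosis, live vaccines and immunocompromise (criteria [26] to [29]).

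**Working it through.** The check is mainly a reading of the provisions side by side, with a little arithmetic on blood volume and exposure.

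**Step 1. Which tests do the criteria need, and what is their status?**

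| Criterion | Test | Markers in Appendix 2 | Required elsewhere? |
|---|---|---|---|
| [19] | HIV | b, c | No |
| [20] | Hepatitis C antibody | b, c | No |
| [21] | Hepatitis B surface antigen | b, c | No |

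So 3 of 3 tests carry footnote b and 0 of 3 are made mandatory. Taking the word *only* in footnote b to govern the timing (at screening and at no other visit) changes nothing, because the condition of clinical indication remains.

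**Step 2. Does any other provision restore the tests?**

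- The Schedule of Activities (Section 2) has a laboratory row at screening that refers to Appendix 2. It has no serology row.
- Section 9.4.1 also refers to Appendix 2 and the Schedule.
- Section 6 bases eligibility on screening laboratory tests, among other things, without naming them.
- Section 8.1.1 begins "If the Sponsor or investigator identifies a subject who did not meet enrollment criteria and was inadvertently enrolled". It governs a known case and does not detect one.

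None of these overrides footnote b.

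**Step 3. Does footnote c show that testing was meant to be routine?** A waiver that asks for a reviewable report sits most naturally beside a default of testing. But b and c can also work together: if a test is indicated and a report from the previous 6 months exists, it need not be repeated. Footnote b suits FSH, which inclusion [1b] needs only for women with 6 to 12 months of amenorrhea. That does not prove that b was misplaced on the other three. Footnote c is therefore a possible sign of intent and no more.

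**Step 4. Does the blood volume help?** First, reproduce Appendix 4 from the Schedule:

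- PK samples: (17 scheduled + 2 extra) × 4 periods = 76
- Laboratory samples: 3 per period × 4 + 1 at follow-up = 13
- Total: 17 × 1 + 11 × 13 + 2 × 76 + 10 × 1 = 17 + 143 + 152 + 10 = 322 mL, rounded up to 330 mL, as stated

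The screening draw exceeds a later laboratory draw by 17 − 11 = 6 mL. The 17 mL is a maximum, and a maximum has to allow for optional tests. The extra 6 mL could cover the serum pregnancy test done at screening, FSH, or serology drawn only when indicated. It is not evidence either way.

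**Step 5. What exposure is at issue?** 4 doses × 20 mg = 80 mg in total. With at least 5 days between doses, the first and last are at least 3 × 5 = 15 days apart. Section 3.3 reports that single doses of 10 to 200 mg were well tolerated, and that 14 days of dosing was generally well tolerated up to 40 mg once daily. The significant adverse events described there arose at 80 mg or more *per day*, which is a different exposure.

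**The case against.** The strongest reply is that there is no contradiction to correct. The criteria do not say that every subject must be tested. Applying them through history and examination, with serology where indicated, is coherent and matches the way inclusion [1] defines a healthy subject. A sponsor may choose that.

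Other provisions also narrow the gap. Inclusion [4] requires laboratory results that are normal or judged not clinically significant, and the panel includes ALT, AST, GGT, bilirubin and lymphocytes with no discretionary footnote. Exclusion [16] covers significant hepatic and hematological disorders, [29] immunocompromise, and [31] anyone whom the investigator or sponsor considers unsuitable. Similar looseness exists elsewhere: [27] names a chest radiograph that the Schedule does not contain, and [18] has no matching test in Appendix 2.

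Most of this stands. It defeats a tempting stronger reading, that footnote b is plainly an error because footnote c and the larger screening draw prove routine testing was intended. The documents do not support that (Steps 3 and 4).

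It does not remove the narrower point. None of these safeguards is a specific test for the three infections, so a carrier with no symptoms and unremarkable routine results passes all of them. And unlike [18] and [27], here the protocol lists the matching test and then expressly makes it optional.

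**Conclusion.** The point holds as a minor one. As written, the protocol allows enrollment without any HIV, hepatitis B or hepatitis C result, so the second limb of [19] to [21] may never be applied to an asymptomatic subject with unremarkable routine laboratory results. This rests on the text of footnote b and on the absence of any overriding provision in the Protocol.

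Two further inferences should be resisted. A reader might conclude that all 32 possible enrollees would go untested, or that a carrier is likely to be enrolled. Thirty-two is only a ceiling: it assumes that no investigator tests anyone and that nobody has a prior report. The documents give no prevalence or testing rate, so no probability can be stated. A reader might also infer harm. The documents show no infection harm at up to four single 20-mg doses and give no harm rate.

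The PK analysis, the sample size and every SAP figure are unaffected. The case for acting is that the change is cheap and makes the criteria and the test list agree.

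**What to change.** In Appendix 2, remove marker b from hepatitis B surface antigen, hepatitis C antibody and HIV, and give them a new note saying that they are done at the screening visit only. Keep footnote c, so that every enrolled subject has either a screening result or a report from the previous 6 months. Leave footnote b on FSH.

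The three assays are already in the panel, and no visit is added. The 17 mL screening maximum and the 322/330 mL totals can stand, on the reasonable assumption that the maximum already allows for a subject in whom all the listed screening tests are drawn.

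There are two costs. One is a small assay charge for subjects who would otherwise not be tested. The other is an occasional false-positive result that loses a healthy volunteer for good, since Section 6.4 states: "Individuals who do not meet the criteria for participation in this study (screen failure) may not be re-screened". The documents give no assay specificity, so that number cannot be estimated.

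If the sponsor does intend discretionary testing, it should say so and explain how the positive-result limb of [19] to [21] is to be applied to a subject who has not been tested.
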